## 9. Subject Accountability

### 9.1. *Point of Enrollment*

Subjects who are confirmed eligible for the study by the CRC (see Section 21.2) and who provided written informed consent are considered enrolled in the study as soon as an attempt is made to insert the LOTUS *Edge* Valve System into the subject's femoral artery.

### 9.2. *Discontinuation of Study Intervention*

If a LOTUS *Edge* valve test device is explanted during conventional scheduled or emergent surgical valve replacement or during an autopsy, if possible, the explanted valve should be assessed by the independent Histopathology Core Laboratory (Section 13.3.4) for macroscopic and microscopic analyses. Please refer to the study Manual of Operations for recommendations on the explant procedure and shipment of the explanted valve.

Information on the explant procedure must be documented in source notes and captured in the Explant Form of the eCRFs.

### 9.3. *Withdrawal*

All subjects enrolled in the clinical study (including those withdrawn from the clinical study or lost to follow-up) shall be accounted for and documented. If a subject withdraws from the clinical investigation the reason(s) shall be reported. Reasons for withdrawal include but are not limited to physician discretion, subject choice to withdraw consent, or death. If such withdrawal is due to problems related to investigational device safety or performance, the investigator shall ask for the subject's permission to follow his/her status/condition outside of the clinical study.

While all efforts will be made to minimize attrition, subjects may withdraw from the study at any time, with or without reason, and without prejudice to further treatment. Withdrawn subjects will not undergo any additional study follow-up, nor will they be replaced. The reason for withdrawal will be recorded (if given) in all cases of withdrawal. The investigator may discontinue a subject from participation in the study if the investigator feels that the subject can no longer fully comply with the requirements of the study or if any of the study procedures are deemed potentially harmful to the subject. Data that have already been collected on withdrawn subjects will be retained and used for analysis, unless local regulations apply. No new data will be collected after withdrawal.

All applicable case report forms up to the point of subject withdrawal and an "End of Study" form for the subject must be completed. If the withdrawal is due to investigator discretion, the investigator should follow-up with the subject per standard of care. Information on determining if a subject is lost to follow-up can be found in Section 9.4.

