#### 6.2.1. Primary Endpoint

The primary endpoint is a composite of all-cause mortality and all stroke at 1 year. The primary analysis set for the primary endpoint is the ITT analysis set.

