### **11.2.3. Reporting Events**

For all subjects, all events that occur from the time of enrollment will be reported. For time based clinical events, the cut-off for events for 30-day endpoints will be 30 days, for 1-year endpoints it will be 365 days, and for 2–10-year endpoints it will be 365 days times the number of years. For events at discharge or 7 days post-procedure, the cut-off for events will be the earlier of the date of discharge or 7 days post-procedure for each subject.

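### Section 9.3 ends all data collection at withdrawal, so later deaths and strokes within the year miss the primary endpoint and can bias the rate low if withdrawal is related to risk

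*Combined protocol and SAP*

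**What the plan says.** Section 6.2.1 defines the outcome: "The primary endpoint is a composite of all-cause mortality and all stroke at 1 year". The primary analysis set is ITT, and Section 11.2.3 sets the event cut-off: "for 1-year endpoints it will be 365 days".

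Section 9.3 on withdrawal:
- "Withdrawn subjects will not undergo any additional study follow-up, nor will they be replaced".
- "No new data will be collected after withdrawal".
- What was gathered before that point is kept: "Data that have already been collected on withdrawn subjects will be retained and used for analysis, unless local regulations apply".
- Discontinuation can come from the site: "The investigator may discontinue a subject from participation in the study if the investigator feels that the subject can no longer fully comply" with the study's requirements, or if study procedures are judged potentially harmful. The rule on new data is not limited to withdrawals chosen by the subject.
- One permission request exists, and only for some withdrawals: "If such withdrawal is due to problems related to investigational device safety or performance". In that case the protocol adds a step: "the investigator shall ask for the subject's permission to follow his/her status/condition outside of the clinical study".

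Section 11.1.1.4 makes the handling of missing outcomes depend on how many there are and on the type of outcome. It commits to sensitivity analyses, with a tipping-point analysis as the example, and refers to the SAP for more. Section 11.1.1.2 plans for 3% attrition: 675 evaluable subjects out of 696 enrolled.

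**The concern.** A subject who withdraws at month 3 and dies at month 6 is in the ITT set, but the death is not in the data. Death and stroke can be ascertained without study visits, so much of this loss is avoidable. It is most clearly avoidable when the investigator ends participation, because the subject need not have withdrawn consent to data collection. Section 9.3 also tells the site to go on seeing such a subject under standard of care. The site may then learn of an event that it cannot record.

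The permission request does not close the gap. It applies only to device-related withdrawals and leads to follow-up outside the study.

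At stake is the pass/fail decision. No control arm shares the loss, so any net under-count goes straight into the comparison with 15.2%.

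**Working it through.** **Inputs.** From Section 11.1.1.2: goal p0 = 0.152, expected rate p1 = 0.111, one-sided alpha 0.025, 675 evaluable, 3% attrition, 696 enrolled. The event rate q among lost subjects is my assumption. The documents do not split the 3% between withdrawal and loss to follow-up, so charging all of it to withdrawal is an upper case.

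**1. The plan's own figures.** For the one-sample z-test with the null standard error in the critical value:

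power = Φ{[(p0 − p1) − 1.96·√(p0(1−p0)/n)] / √(p1(1−p1)/n)}

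With n = 675 this is Φ{(0.041 − 1.96 × 0.01382)/0.01209} = 87.5%, as stated. Enrolment is 675/0.97, which rounds up to 696, leaving 21 subjects missing. The sample size has no error.

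**2. Success limits.** p0 − 1.96·√(p0(1−p0)/n) is 0.1249 at n = 675 and 0.1253 at n = 696. Success therefore needs at most 84 of 675 or 87 of 696 events. At a true rate of 15.2%, P(X ≤ 84 | n = 675) = 2.4%.

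**3. Lost subjects excluded from the denominator.** The full-cohort rate is held at 15.2% and a fraction d is lost. The rate among those observed is (0.152 − d·q)/(1 − d). False success is the exact binomial probability of meeting the limit.

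| d | assumed q | observed rate | false success |
|---|---|---|---|
| 3% | 10% | 15.36% | 1.8% |
| 3% | 15.2% | 15.20% | 2.4% |
| 3% | 20% | 15.05% | 3.1% |
| 3% | 30% | 14.74% | 4.9% |
| 3% | 40% | 14.43% | 7.6% |
| 1% | 30% | 15.05% | 3.1% |

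Worked row: (0.152 − 0.03 × 0.30)/0.97 = 0.1474, and P(X ≤ 84 | n = 675) = 4.9%.

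**4. Lost subjects kept as event-free.** Even if withdrawal is unrelated to risk, the observed rate is 0.97 × 0.152 = 14.74%, and P(X ≤ 87 | n = 696) = 5.1%.

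**5. Bias at the expected rate.** Take completers at 11.1% and 3% lost. If the lost subjects have twice the risk, the full-cohort rate is 0.97 × 11.1 + 0.03 × 22.2 = 11.43%, so the completers' rate is 0.33 points low. At three times the risk it is 0.67 points low. The testing margin is 4.1 points.

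**6. How many lost events would change the result.** With 75 of 675 observed (11.1%), success survives up to 87 of 696. That leaves room for 87 − 75 = 12 more events, so 13 of the 21 (62%) would have to be events. With 84 of 675 observed, the room is 3, and 4 events would reverse the result.

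**The case against.** A reader might infer that the device rate is certainly biased low, or that lost events can only favour the device. The documents do not support that. When lost subjects are excluded, the bias is zero if withdrawal is unrelated to risk, and it reverses if they are at lower risk (1.8% false success at a 10% event rate). Nothing in the text says that withdrawn subjects count as event-free, and nothing says that they are the sickest. Inability to comply is a plausible marker of risk, not a documented one.

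Other points on the plan's side also stand:
- Not all of the 3% need be withdrawals. Loss to follow-up is a separate route: Section 9.4 does not allow it to be declared before the 1-year visit and requires three contact attempts. Section 10.10 has the site try the telephone when an in-person visit cannot be done.
- A stroke recorded before withdrawal still counts.
- The planned sensitivity analyses would show how fragile a result is, and at the expected rate success is robust.
- No separate SAP text is among the documents. It may fix the missing-outcome rule, and with it the direction and size of any bias.

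None of this restores the endpoint data. The Section 9.4 protections do not apply to a withdrawn subject, and a tipping-point analysis tests assumptions about events without recovering them.

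**Conclusion.** The gap is real and modest. Section 9.3 keeps deaths and strokes after withdrawal out of the ITT primary endpoint. Whether that lowers the rate depends on two things that the documents leave open: whether withdrawal is related to risk, and how withdrawn subjects enter the denominator.

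At the goal boundary with 3% lost, false success ranges from 1.8% to 7.6% over assumed event rates of 10% to 40%, against 2.4% with no bias. It is 5.1% if the lost subjects are counted as event-free. With 1% lost at a 30% event rate it is 3.1%. A result near 11.1% would be safe; a result near the limit of 84 of 675 would not. This is a cheap improvement worth making, not a flaw that undermines the design.

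**What to change.** In Section 9.3, replace the blanket rule on new data:
- Separate the end of study visits from withdrawal of consent for data. Investigator-initiated discontinuation should end visits only.
- Ask every withdrawing or discontinued subject, not only those with device-related reasons, for consent to a vital-status and stroke check at 1 year by telephone, treating physician or records.
- Allow searches of public death records where local law permits.
- State that events found by day 365 count in the ITT analysis.

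The cost is protocol and consent wording, plus a call or record check for at most about 21 subjects. Some may decline, so recovery will be partial. If status were obtained on all 696, power at 11.1% would rise from 87.5% to 88.6% by the formula in step 1.

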#### 9.5. *End-of-Study Definition*

This clinical trial will be considered completed when subjects are no longer being examined or the last subject’s last study visit as outlined in the data collection schedule (**Table 10.1-1**) has occurred. All subjects who receive a study device will be evaluated at discharge or 7 days (whichever comes first), 30 days, and annually up to 10 years post index procedure. Visits at 30 days, 1–5 years, 7 years and 10 years are office/in-person visits. Telephone follow-up is allowed at 6, 8, and 9 years. A subject’s participation in the study will be considered complete after the 10-year visit. For subjects who do not receive a study device, participation in the study will be considered complete after the 1-year visit.

## 10. Study Methods

### 10.1. *Data Collection*

This section indicates the data needed to fulfill the objectives of this clinical study. Boston Scientific Corporation considers data collected from clinical trial subjects to be personal data (see definitions of different data categories in **Table 25.2-1**) and compliance with privacy and data protection laws and regulations (for example, the General Data Protection Regulation [GDPR]) to be critically important. Data collection for this clinical study has been carefully considered to comply with data privacy laws.

The study event schedule is shown diagrammatically in **Figure 10.1-1** and discussed in **Table 10.1-1** and Section **10.2** through Section **10.11**. The methods are based on VARC metrics, recommendations in the 2012 ACCF/AATS/SCAI/STS Expert Consensus Document on Transcatheter Aortic Valve Replacement and the 2014 AHA/ACC Guideline for the Management of Patients With Valvular Heart Disease.

[figure not shown]

Figure 10.1-1: REPRISE IV Data Collection Scheme

**Table 10.1-1: Study Event Schedule**

Assessment	Screening a	Baseline	Procedure	Within 1 Day Post-procedure	Prior to Discharge or 7 Days Post-Procedure	30 Days b (±7 Days) Office Visit	12 Months b (±30 Days) Office Visit	24–60 Months b [Annual] (±45 Days) Office Visit	84 and 120 Months b (±60 Days) Office/In person Visit	72, 96, and 108 Months b (±60 Days) Telephone
Signed Informed Consent Form c	X	–	–	–	–	–	–	–	–	–
Demographics and medical history, including cardiac, neurological, renal (e.g., creatinine) and peripheral disease	X	–	–	–	–	–	–	–	–	–
NYHA Classification	X	–	–	–	X	X	X	X	X	–
NIHSS d	–	X	–	–	X	–	X	–	–	–
Modified Rankin Scale d	–	X	–	–	X	X	X	X	–	–
12-lead ECG e	X	–	–	X	X	X	X	–	–	–
Laboratory tests f	–	X	–	X	–	–	–	–	–	–
Risk assessments g	X	–	–	–	–	–	–	–	–	–
Frailty, disability and comorbidity h	X	–	–	–	–	–	X h	–	–	–
Antiplatelet and anticoagulant (if applicable) medications	X	–	X	–	X	X	X	X	X	X
Other CV medications	X	–	–	–	–	–	–	–	–	–
TTE i	X	–	–	–	X	X	X	X	X	–
TEE j	–	–	O	–	–	–	–	–	–	–
Coronary angiogram/CT coronary angiogram k	X	–	–	–	–	–	–	–	–	–
CT angiogram of aortic structure l	X	–	–	–	–	X m	–	–	–	–
CT angiogram of iliofemoral system n	X	–	–	–	–	–	–	–	–	–
QOL surveys o	–	X	–	–	–	X	X	X p	–	–

**Table 10.1-1: Study Event Schedule**

Assessment	Screening a	Baseline	Procedure	Within 1 Day Post-procedure	Prior to Discharge or 7 Days Post-Procedure	30 Days b ( $\pm 7$ Days) Office Visit	12 Months b ( $\pm 30$ Days) Office Visit	24–60 Months b [Annual] ( $\pm 45$ Days) Office Visit	84 and 120 Months b ( $\pm 60$ Days) Office/In person Visit	72, 96, and 108 Months b ( $\pm 60$ Days) Telephone
Procedural cine-angiography (including post-deployment aortogram) q	–	–	X	–	–	–	–	–	–	–
AE and ADE assessments r	–	–	X	X	X	X	X	–	–	–
Device deficiencies, SAE, SADE, UADE and CEC event assessments s	–	–	X	X	X	X	X	X	X	X
4D CT (Imaging Substudy only) t	–	–	–	–	–	X	X	–	–	–

**Note 1:** X = required; O = optional; – = not required; follow-up should be done by study personnel or as noted below.

a: Screening materials for CRC review should be submitted electronically at least 5 days in advance of CRC review.

b: All follow-up dates will be calculated from the date of the (attempted) index procedure. Where indicated, visits must be an office/clinical/in person visit but may be done in-hospital should the subject be admitted at the time. Subjects who are enrolled but do not receive a study device will be followed for 1 year to assess for safety but do not need to have protocol required TTE or ECG.

c: Study-specific consent includes screening consent to perform required assessments that will be evaluated by the CRC to confirm subject eligibility. If the study Informed Consent Form is modified during the course of the study, study subjects will be re-consented as necessary.

**Note 2:** The subject should undergo the index procedure within 30 days after signing the study Informed Consent Form.

d: NIHSS and mRS must be performed by a neurology professional or certified personnel (external certification for NIHSS; internal or external certification for mRS). The NIHSS and mRS assessors should be independent (not involved with the care of study subjects). For subjects diagnosed with a stroke, a neurological physical exam, mRS, and NIHSS must be performed after the event; mRS must also be administered at  $90 \pm 14$  days after a stroke; the simplified mRS questionnaire may be used for this follow-up assessment. The neurological physical examination must be performed by a neurologist, neurology fellow, neurology physician assistant, or neurology nurse practitioner who is independent of the study. If a subject who has not received a study device experiences a stroke within the first 1 year after the index procedure, mRS must be performed on that subject after the event; mRS must also be administered at  $90 \pm 14$  days after a stroke and the results must be reported to the Sponsor.

e: All screening and post-procedure 12-lead ECGs must be performed according to the ECG Core Laboratory guidelines (see study Manual of Operations). If the subject is enrolled, the ECG must be provided to the Core Laboratory.

f: Laboratory tests at baseline include CBC with platelets, albumin, serum creatinine, and cardiac enzymes. Cardiac enzymes (CK is required, CK-MB or troponin if CK is elevated) must be collected twice at intervals per standard of care within 6-24 hours post-procedure. Acute kidney injury (AKI) should be assessed through discharge/7 days based on the AKIN system.

**Table 10.1-1: Study Event Schedule**

Assessment	Screening a	Baseline	Procedure	Within 1 Day Post-procedure	Prior to Discharge or 7 Days Post-Procedure	30 Days b (±7 Days) Office Visit	12 Months b (±30 Days) Office Visit	24–60 Months b [Annual] (±45 Days) Office Visit	84 and 120 Months b (±60 Days) Office/In person Visit	72, 96, and 108 Months b (±60 Days) Telephone
------------	------------------------	----------	-----------	-----------------------------	---	---	--	--	--	--

- g: Consists of STS score, euroSCORE II, and heart team assessment including an in-person evaluation by a center cardiac surgeon that must be confirmed by the CRC (which must include an experienced cardiac surgeon).
- h: Frailty, disability, and comorbidity risk assessments must be captured at screening: height, weight, strength and balance (use of wheelchair, gait speed to walk 5 meters, number of falls in the past 6 months, maximal grip strength), and activities of daily living (Katz Index); at 1 year, gait speed to walk 5 meters must be assessed again.
- i: Transthoracic echocardiogram (TTE) is required for all subjects who have a study valve implanted in the aortic position. This includes assessment of EOA, peak and mean aortic valve pressure gradients, peak aortic velocity, aortic regurgitation assessment, and LVEF. Screening TTE must be performed within 60 days prior to CRC approval. At least 1 echocardiogram must be obtained before discharge or 7 days (whichever comes first); if multiple echocardiographic studies are performed prior to discharge and within 7 days of the procedure, the latest study performed will be used for analysis. All TTEs must be performed according to the Echocardiography Core Laboratory procedure guidelines (see study Manual of Operations). If a subject does not receive an implanted study valve, then no follow-up TTE is required.  
**Note 3:** In cases of low flow low gradient aortic stenosis with left ventricular dysfunction (ejection fraction <50%), dobutamine can be used to assess the grade of aortic stenosis; the subject may be enrolled if echocardiographic criteria are met with this augmentation. In cases where a subject who has met the echocardiographic criteria for enrollment receives BAV prior to the index procedure and subsequently no longer meets the REPRISE IV aortic valve pressure gradient or EOA criteria, the subject may still be enrolled based on the pre-BAV echocardiographic data. In such cases, the most recent echocardiogram done prior to the index procedure (even if after BAV) must be submitted to the Echocardiography Core Laboratory to be included in the baseline data.
- j: TEE can be performed at the discretion of the operator.
- k: A coronary angiogram/CT coronary angiogram must be performed within 365 days prior to CRC approval. If there is concern regarding the current extent of coronary artery disease or aortic stenosis, the CRC may recommend a repeat study closer to the time of enrollment.
- l: A CT angiogram of the aortic complex must be performed within 180 days prior to CRC approval (and should be performed within 90 days if possible) to evaluate the aortic valve anatomy and aortic root dimensions for device sizing. CT angiogram must be performed according to the CT/X-ray Core Laboratory procedure guidelines (see study Manual of Operations). It must be sent to the Core Laboratory for detailed measurements and analyses in advance of the CRC review where results will be assessed to confirm subject’s eligibility.
- m: For subjects in the Bicuspid Nested Registry Cohort, a computed tomography scan at 30 days post LOTUS *Edge* valve implantation. Please refer to the CT Core Laboratory procedure guidelines (see study Manual of Operations). Results must be sent to the CT Core Laboratory.
- n: An assessment of the iliofemoral system must be performed within 180 days prior to CRC approval (and should be performed within 90 days if possible). A CT angiogram of the iliofemoral system should be performed for complete visualization of the iliac and femoral arteries to assess for dimensions, tortuosity, and calcification. The CT angiogram should be performed per the procedure guidelines (see study Manual of Operations) and sent to the CT

**Table 10.1-1: Study Event Schedule**

Assessment	Screening a	Baseline	Procedure	Within 1 Day Post-procedure	Prior to Discharge or 7 Days Post-Procedure	30 Days b (±7 Days) Office Visit	12 Months b (±30 Days) Office Visit	24–60 Months b [Annual] (±45 Days) Office Visit	84 and 120 Months b (±60 Days) Office/In person Visit	72, 96, and 108 Months b (±60 Days) Telephone
------------	------------------------	----------	-----------	-----------------------------	---	---	--	--	--	--

Core Laboratory with the screening CT angiogram of the aortic structure. An iliofemoral invasive angiogram may be substituted for the iliofemoral CT angiogram.

- o: Includes the Kansas City Cardiomyopathy and SF-12 QOL questionnaires. Baseline QOLs should be performed within 30 days prior to the index procedure.
- p: QOL survey at 60 months.
- q: Procedural cine-angiogram including the baseline images of the aortic complex and the final post-deployment aortogram of the ascending aorta must be performed and sent to the CT/X-Ray Core Laboratory for analysis.
- r: AEs and ADEs will be monitored and collected from the time of enrollment through 12-month follow-up. For subjects who do not receive the study device, AEs will be monitored through 12-month follow-up.
- s: Information on device deficiencies for the test device(s) will be monitored and reported to Boston Scientific. Information on all SAEs, SADEs, UADEs, and CEC events will be monitored and reported to Boston Scientific for enrolled subjects from the time of enrollment through 5 years. After 5 years, serious adverse event assessment (includes SAE, SADE, UADE, and relevant VARC events to be adjudicated by the CEC [see *Note 4* below]) for test device(s) and device deficiencies assessment for test device(s) with associated treatment will be monitored and reported to Boston Scientific for enrolled subjects through termination of the study. For subjects who do not receive a study device, the aforementioned events will be monitored through 1-year post-index procedure. Please refer to Section 6.2.2 for a list of CEC events and Table 25.2-1 for definitions of these events, which specify data required for CEC adjudication. Complaint reporting of any device deficiencies for any commercially available products used should be carried out using the manufacturer’s processes.  
*Note 4:* Relevant VARC events after 5 years to be adjudicated by the CEC include the following: mortality, stroke, spontaneous myocardial infarction, acute kidney injury, repeat procedure for valve-related dysfunction, hospitalization for valve-related symptoms or worsening congestive heart failure (NYHA III or IV), new pacemaker, new onset atrial fibrillation or atrial flutter, prosthetic aortic valve malpositioning (valve migration, valve embolization, or ectopic valve deployment), TAV-in-TAV, prosthetic aortic valve thrombosis and endocarditis.
- t: For subjects in the CT Imaging Substudy, a 4D CT scan at 30 days and at 1-year post LOTUS *Edge* valve implantation must be done. Please refer to the CT Core Laboratory procedure guidelines (see study Manual of Operations). The data must be sent to the independent CT core laboratory.

